### **4.1.1 Other considerations for randomisation**

#### **4.1.1.1 Oral examination**

In several biological programs, there have been serious infections and/or death related to Ludwig's angina. Although this has not been seen in the anifrolumab program, Investigators should check a subject's oral cavity and review their dental health carefully. While a dental examination is not required prior to randomisation in this study, Investigators are cautioned to consider carefully whether subjects have active caries or a dental infection prior to randomisation that might impact subject safety.

#### **4.1.1.2 Mammography**

As subjects with SLE have impaired immune response, are treated with immunosuppressants, and are at potential risk for malignancy, it is recommended that subjects randomised into the LTE study are compliant and up to date with local recommendations for mammography or other screening procedures for breast cancer.

## **4.2 Treatment period**

During the treatment period, visits will be scheduled for each Q4W administration.

Procedures during the Treatment Period Year 1 will be performed according to the Study Plan detailing the procedures (Table 2). Procedures during the Treatment Period Year 2 through Year 3 will be performed according to the Treatment Period Study Plan detailing the procedures (Table 3). The subject-reported outcome assessments should be completed by the subject (unassisted by spouse, family members, or friends) prior to all other evaluations and prior to the infusion, as disease assessments/clinical evaluations may confound the results.

#### 4.2.1 Premature discontinuation of investigational product

Subjects who prematurely discontinue investigational product (see Section 3.9.1) will be asked to return for all regularly scheduled clinic visits. If the subject is unwilling to complete all regularly scheduled clinic visits, the subject should complete the Early Discontinuation Visit (EDV, Week 156) within 4 weeks after the last administration of investigational product, as well as Follow-up Visit 1 and Follow-up Visit 2 (8 and 12 weeks after the last dose of investigational product) unless consent is withdrawn. If the subject is unwilling to continue with any study visits, including EDV, or is willing to continue with only selected study assessments, at a minimum, the following assessments should be completed:

- AEs including AESIs and SAEs
- [REDACTED]
- Serum chemistry, haematology, urinalysis
- Urine for protein, creatinine, and urine-protein-creatinine ratio
- Vital signs
- Physical examination, weight
- [REDACTED]
- [REDACTED]
- Concomitant medications
- Blood test for TB
- Pap smear test (female subjects with an intact cervix only)

If the subject does not agree to do this, they will be asked if they can be followed on a monthly basis via telephone calls. At these calls, they will be asked about AEs/SAEs, lupus symptoms, and lupus medications.

Adverse events will be followed up per Section 6.6.2.

#### 4.3 Unscheduled visit

There may be times a subject needs to have an unscheduled visit. The Investigator should determine the assessments to be completed based on the reason for the unscheduled visit and for subject safety. Concomitant medications and AEs should be completed whenever a subject has an unscheduled visit.

If a subject presents for an unscheduled visit in lieu of a regularly scheduled visit (ie, the subject is seen for safety and efficacy assessments when a regularly scheduled dosing or follow-up visit is missed), the Investigator should complete all possible safety and efficacy assessments applicable to the missed visit. Unscheduled efficacy assessments should not be collected in between completed regular study visits.

#### **4.4 Follow-up period**

Procedures will be performed according to the Follow-up Period Study Plan (Table 4).

Subjects who are withdrawn from the study, and do not agree to complete the 156-week study period, and do not agree to complete the 3-year study period, should complete the EDV (Week 156 procedures) and be followed 8 and 12 weeks after the last administration of investigational product by completing the Follow-up Visits 1 and 2 assessments (see Section 3.9).

### **5. STUDY ASSESSMENTS**

The Investigator will ensure that data are recorded on the CRFs as specified in the study protocol and in accordance with the instructions provided.

The Investigator ensures the accuracy, completeness, and timeliness of the data recorded and the provision of answers to data queries according to the Clinical Study Agreement (CSA). The Investigator will sign the completed CRFs. A copy of the completed CRFs will be archived at the study site.

A Laboratory Manual will be provided to the sites that specifies the procedures for collection, processing, storage, and shipment of samples, as well as laboratory contact information, specific to this clinical research study.

[REDACTED]

[REDACTED]

[REDACTED]

[REDACTED]

[REDACTED]

[REDACTED]

[REDACTED]

[REDACTED]

[REDACTED]

[REDACTED]

[REDACTED]

[REDACTED]

[REDACTED]

[REDACTED]

[REDACTED]

[REDACTED]

[REDACTED]

[REDACTED]

## 5.2 Safety assessments

Key safety assessments are AESIs and SAEs, which will be assessed at every study visit. All AEs will also be collected at every study visit. Investigators should apply local practices for safety monitoring, eg, by serum chemistry tests, in case SOC dose is changed, eg, increased, and/or new DMARD is added.

In addition, vital signs, physical examination, safety laboratory tests, and electrocardiograms (ECGs) will be assessed at the times indicated in the Study Plan (see [Table 2](#) for assessments to be performed for Treatment Period Year 1, [Table 3](#) for Treatment Period Year 2 to 3, and [Table 4](#) for the Follow-up Period).

### 5.2.1 Adverse events

Adverse events, SAEs, and AESIs are defined in Sections [6.1](#), [6.2](#), and [6.5](#), respectively.

Recording of AEs is described in Section [6.6](#), and reporting of SAEs and AESIs is described in Sections [6.7](#) and [6.8](#), respectively.

### **5.2.2 Vital signs**

Vital signs (oral temperature, blood pressure, pulse rate, and respiratory rate) will be obtained at each visit. Specific information on vital signs surrounding the infusion is included in Section 7.2.4 (Subject monitoring/procedures during and after infusions).

### **5.2.3 Physical examination**

A physical examination will be performed at the visits specified in the Study Plan (Table 2, Table 3, and Table 4) and will include an assessment of the following: general appearance, head and neck, breast, respiratory, cardiovascular, abdomen, musculoskeletal/extremities, neurological, skin, lymph nodes, and thyroid. Body height will be captured at randomisation only. Subjects will be weighed at each study visit. Medically significant changes from randomisation in the LTE study on physical examination will be recorded as AEs.

### **5.2.4 Pap smear**

Most cases of cervical cancer appear to be related to papilloma virus infection. Because of the potential for viral reactivation due to blockade of the Type 1 IFN pathway, we are assessing cervical dysplasia in this study, although to date there has been no signal in the anifrolumab studies. Females with an intact cervix must have a Pap smear completed and without documented malignancy (eg. no signs of CIN grade III, CIS, or AIS) within 90 days before Day 1 or up until 30 days after randomization, ie before dosing at V2. Pap smears should thereafter be performed yearly and all female subjects with an intact cervix should have a Pap smear performed within 3 months of the last IP dose, eg, at the end of study or at the early discontinuation visit.

Subjects with abnormal Pap smear results of atypical squamous cells of undetermined significance, atypical squamous cells where high-grade squamous intraepithelial lesion (HSIL) cannot be ruled out (ASC-H), atypical glandular cells (AGC), or CIN grades I and II (CIN I and II) will be allowed to enter the study: [REDACTED]. If the subject's gynaecologist has recommended a repeat Pap smear be performed at a specified interval, the Pap smear should be obtained as recommended and the report provided in the source document. Since access to a Pap smear may vary by country, the Sponsor recommends that local guidelines are used for obtaining routine follow-up Pap smears in females who have received immunomodulators or immunosuppressive treatment.

### **5.2.5 Assessment of cardiovascular risk**

To understand the contribution of the chronic inflammatory response in SLE to dyslipidaemia (as a potential risk for accelerated subclinical arteriosclerotic cardiovascular disease) and the potential effects of anifrolumab treatment, both lipid (including low- and high-density lipoproteins and triglycerides [see Section 5.2.9]) and inflammatory profiles will be obtained during the study. Concomitant medications received for cardiovascular indications should be collected and recorded.

### 5.2.6 Electrocardiogram

Digital ECGs for all subjects at all centres will be conducted at the centre using a machine provided by the central ECG vendor and will be transmitted to the central ECG laboratory. Digital ECGs will be performed at the visits specified in the Study Plan (Table 2 and Table 3). Digital ECGs will be obtained after the subject has been resting in a supine position for at least 10 minutes. All digital ECGs will be documented by recording the date, time, heart rate, QRS duration, PR interval, RR interval, QT, and corrected QT interval. The corrected QT intervals will be calculated using the Fridericia formula.

The Investigator or qualified designee will judge the overall interpretation as normal or abnormal. If abnormal, it will be decided as to whether or not the abnormality is clinically significant or not clinically significant, and the reason for the abnormality will be recorded on the CRF, if the Investigator considers it clinically significant. Abnormal values shall not be recorded as AEs unless deemed clinically significant.

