### **6.1 Definition of adverse events**

An AE is the development of an undesirable medical condition or the deterioration of a pre-existing medical condition following or during exposure to a pharmaceutical product, whether or not considered causally related to the product. An undesirable medical condition can be symptoms (eg, nausea, chest pain), signs (eg, tachycardia, enlarged liver) or the abnormal results of an investigation (eg, laboratory findings, ECG). In clinical studies, an AE can include an undesirable medical condition occurring at any time, including run-in or washout periods, even if no study treatment has been administered.

The term AE is used to include both serious and nonserious AEs.

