#### **6.6.6 Adverse events based on examinations and tests**

The results from protocol-mandated laboratory tests and vital signs will be summarised in the Clinical Study Report. Deterioration as compared to baseline in protocol-mandated laboratory values, vital signs, ECGs, and other safety assessments should therefore only be reported as AEs if they fulfil any of the SAE criteria or are the reason for discontinuation of treatment with the investigational product.

If deterioration in a laboratory value/vital sign is associated with clinical signs and symptoms, the sign or symptom will be reported as an AE and the associated laboratory result/vital sign will be considered as additional information. Wherever possible, the reporting Investigator will use the clinical rather than the laboratory term (eg, anaemia versus low haemoglobin value). In the absence of clinical signs or symptoms, clinically relevant deteriorations in non-mandated parameters should be reported as AE(s).

Deterioration of a laboratory value, which is unequivocally due to disease progression, should not be reported as an AE.

Any new or aggravated clinically relevant abnormal medical finding at a physical examination as compared with the baseline assessment will be reported as an AE (or SAE, as appropriate).

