#### **4.2.1.4 ECGs**

The number and percentage of subjects with normal; abnormal, not clinically significant; and abnormal, clinically significant ECG results will be presented as a shift table from baseline to last on-treatment value.

Observed values and changes from baseline of ECG values will be summarised by parameter and visit using descriptive statistics. The summary statistics presented will be minimum, 1st quartile, median, 3rd quartile, maximum, mean, and SD.

For each ECG parameter with available criteria, the number and percentage of subjects with Potentially Clinically Significant post-baseline values and Potentially Clinically Significant changes from baseline, respectively, will be presented by parameter and criterion.

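### Protocol 5.2.6 and 6.6.6 set different tests for recording an ECG finding as an AE, and the SAP's last-value ECG category table does not fully cover the gap

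*Protocol*

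**What the plan says.** **When an ECG finding is an AE.**
- Protocol 5.2.6 has the investigator classify each ECG as normal or abnormal and, if abnormal, as clinically significant or not. For a clinically significant abnormality the reason goes on the CRF. It then states: "Abnormal values shall not be recorded as AEs unless deemed clinically significant".
- Protocol 6.6.6 covers deterioration in protocol-mandated assessments and names ECGs: "ECGs, and other safety assessments should therefore only be reported as AEs if they fulfil any of the SAE criteria". Its one alternative route to AE status is a change that caused the subject to stop investigational product.
- Protocol 6.1 lists an abnormal ECG among investigation results that can constitute an AE.
- Protocol 5.2.1 refers readers to Section 6.6 for the recording of AEs in general.

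**How ECGs are tabulated.**
- SAP 3.1.4 combines the central reading and the investigator's judgement into three ranked categories: normal; abnormal, not clinically significant; abnormal, clinically significant. The investigator prevails where the two differ.
- SAP 4.2.1.4 summarises that category once: "clinically significant ECG results will be presented as a shift table from baseline to last on-treatment value".
- The same section summarises continuous ECG variables by visit and counts subjects with potentially clinically significant (PCS) post-baseline values or changes.
- SAP Section 3 sets baseline at the feeder-study baseline. SAP 3.1 ends the on-treatment period 28 days after the last dose.

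**The concern.** Take a scheduled ECG that the investigator calls clinically significant, that meets no seriousness criterion and that does not stop treatment. A site following 5.2.6 would record an AE. A site following 6.6.6 would not. Both sites could believe they had complied with the protocol.

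The study makes no formal comparison and reports rates for each group separately. Events left unrecorded therefore lower the reported rate directly, and the reader cannot tell a low rate from incomplete capture. AEs and ECGs are both named safety variables (Protocol 8.4.1, SAP 3.1). If the ECG tables showed every finding judged significant, the AE ambiguity would matter less. The question is whether they do.

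**Working it through.** The documents give no figure to reproduce here. The check is a comparison of text, followed by day arithmetic.

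**1. The two rules side by side, for a scheduled ECG**

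| Finding | 5.2.6 (natural reading) | 6.6.6 |
|---|---|---|
| Clinically significant and serious | AE | AE |
| Clinically significant, reason for stopping treatment | AE | AE |
| Clinically significant, neither of these | AE | not an AE |
| Not clinically significant, not serious, not the reason for stopping | not an AE | not an AE |

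The third row is the conflict.

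**2. Does other text resolve it?**
- The symptoms clause of 6.6.6 begins "If deterioration in a laboratory value/vital sign is associated with clinical signs and symptoms". It does not name ECGs, and it makes the symptom the AE rather than the test result.
- The 6.6.6 clause on clinically relevant deterioration without symptoms is confined to non-mandated parameters. Scheduled ECGs are mandated.
- Protocol 5.2.9 sends sites to Section 6.6 for AEs based on laboratory tests. Protocol 5.2.6 has no such pointer and states its own rule.
- The pointer in 5.2.1 is general and sets no precedence.

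**3. Does the SAP recover the finding?** Compare the planned categorical summaries:
- Vital signs: shifts from baseline to maximum and minimum post-baseline values (SAP 4.2.1.2).
- Laboratory values: shifts to maximum and minimum on-treatment values (SAP 4.2.1.6).
- Urinalysis: shift to the last on-treatment value, plus treatment-emergent change at any post-baseline value (SAP 3.1.6, 4.2.1.6).
- ECG category: shift to the last on-treatment value only (SAP 4.2.1.4).

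Of these four, only the ECG category lacks an any-time view.

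**4. How many ECGs enter the category table?**
- Inputs: ECGs at LTE Weeks 0 and 52 (Protocol Table 2) and Weeks 104 and 156 (Protocol Table 3); last planned dose at Week 152; visit window of 7 days either way.
- LTE day = 7 × week + 1. Weeks 0, 52, 104 and 156 give days 1, 365, 729 and 1093. Week 152 gives day 1065.
- End of the on-treatment period with dosing on schedule: 1065 + 28 = 1093.
- Week 156 window: 1093 − 7 = 1086 to 1093 + 7 = 1100.
- Because baseline is the feeder-study baseline, all four LTE ECGs are post-baseline for a Randomised Anifrolumab 300 mg subject.
- Week 156 ECG by day 1093: it is the last on-treatment scheduled ECG, and Weeks 0, 52 and 104 stay out of the table.
- Week 156 ECG on days 1094 to 1100: it is off treatment. Week 104 becomes the last scheduled value, and Weeks 0, 52 and 156 stay out.
- Either way, three of the four scheduled ECGs are not shown. A later unscheduled on-treatment ECG would displace the fourth, hence at least three.

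**5. Illustration.** Assume a significant category appears at exactly one of k equally likely on-treatment ECGs. The last-value table then misses (k − 1)/k: 2/3 = 67% for k = 3, 3/4 = 75% for k = 4, 4/5 = 80% for k = 5. This shows the mechanism. It is not an estimate for the trial, because the documents give no frequency or duration of ECG findings.

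**The case against.** **The sections can be reconciled.** Section 5.2.6 is worded negatively, so read literally it sets a necessary condition and no duty to record. Section 6.6.6 adds another, and 5.2.1 points to Section 6.6. A site could meet both by recording only findings that are clinically significant and also satisfy 6.6.6. This reading is possible, but it is not the natural one, and no text tells a site to combine the conditions. The conflict stands.

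**The effect is contained.** This largely stands. A reader might infer that cardiac AE rates become uninterpretable; the documents do not support that. The affected set is non-serious ECG findings that do not stop treatment. The primary variables are AESIs and SAEs, and MACE adjudication draws on deaths and cardiovascular SAEs (Protocol 6.5.7). Symptoms and diagnoses are still collected under 6.6.5. Investigators and site staff stay blinded, so nothing suggests that the rule a site follows would differ by arm.

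**The information is not all lost.** This also stands in part. A reader might infer that every transient ECG finding disappears. That is not so: the reason for a clinically significant abnormality is on the CRF, LTE data are listed (SAP 4.1.3), and transient numeric changes can appear in the by-visit and PCS tables. The PCS criteria are redacted, so their exact coverage cannot be stated. What the planned tables omit is the investigator's overall category at any ECG other than the last on treatment.

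**A last-value shift is a legitimate choice.** It is, and it can stay. The point is that it is the only summary of this category.

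**Conclusion.** The two protocol sections give different answers for one defined class of finding, and nothing settles which applies. Recording may therefore vary by site, and the completeness of non-serious ECG-based AE rates is uncertain. The number of affected findings cannot be derived from the documents.

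The SAP only partly compensates. For a Randomised Anifrolumab 300 mg subject completing Week 156, at least three of the four scheduled LTE ECGs do not contribute to the only category table. That count assumes the scheduled ECGs were done and dosing ran to Week 152 on schedule.

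The conclusion rests on reading 5.2.6 as making a clinically significant ECG abnormality recordable, which agrees with 6.1. It is a moderate point about secondary safety reporting and does not undermine the primary objective.

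**What to change.** **Protocol.** Reconcile 5.2.6 and 6.6.6 so that one rule governs when an ECG finding is recorded as an AE, and cross-refer the two sections. Which threshold to adopt is for the sponsor to decide. The cost is a new protocol version with any approvals that Section 10.5 requires. The study was expected to end by Q3 2021 (Protocol 9.3) and SAP v5.0 is dated 14 April 2022. If the study ended near schedule, rewording cannot restore findings already not recorded as AEs.

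**SAP 4.2.1.4.** Beside the last-value shift, add a shift from baseline to the worst on-treatment ECG category, using the ranking already in SAP 3.1.4, or present the category by visit. The cost is one extra table. It needs no new data, because the judgement is made for each abnormal ECG, and it does not depend on which AE rule a site followed. It is therefore the more useful of the two changes at this stage.

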### 5.2.7 Tuberculosis monitoring

Blood testing for TB will be done using the interferon-gamma release assay (IGRA) test (ie, QFT-G In-Tube Test). Evaluation of all subjects by QFT-G In-Tube Test will be performed by the central clinical laboratory according to the Study Plan (Table 2 and Table 3). Annual QFT-G testing is required for all study subjects.

Compared to culture-confirmed TB, overall, 87.6% of subjects have a positive QFT-G In-Tube Test result (Cellestis, 2005). The false negative rate in this setting appears to be over 12%. Further, the performance of the test in the setting of immunosuppressant drugs has not been evaluated. Nor has it been evaluated in individuals with medical conditions other than, or in addition to, latent TB, or TB disease. The guide also states that “Medical treatments or conditions that impair immune functions can potentially reduce IFN- $\gamma$  responses and prevent detection of a specific response to the (secretory proteins) ESAT-6 and CFP-10 (the test stimulators).”

#### 5.2.7.1 Tuberculosis results at time of randomisation/Week 52 of the Phase 3 Study D3461C00004 or D3461C00005

- If the QFT-G test result was **negative** and there is no known history of recent exposure to individuals with active TB, the subject may be randomised.
- If the QFT-G test result was **newly positive**, a chest x-ray must be performed. If the chest x-ray shows no evidence of active TB, and the subject has no symptoms or medical history consistent with active TB, the subject must have a retest. If the retest is positive, the subject must start on prophylaxis within 30 days of randomisation, but prior to the second dose (Visit 2/Week 4) in the LTE study. The subject should be referred to a TB specialist. If a TB specialist is not available, the local country guidelines should be followed for further diagnostic work up and anti-TB treatment regimens. If no local guidelines exist for immunocompromised

individuals, then USA guidelines may be followed. This should be reported as an AESI. The QFT-G test must be repeated annually.

- If the QFT-G test was **positive but not newly positive**, the subject must have been diagnosed with latent TB and must have documentation confirming completion of appropriate OR initiate treatment for latent TB within 30 days of randomisation, but prior to the second dose (Visit 2/Week 4).
- If the QFT-G test result was newly indeterminate (as confirmed on retest unless prior positive QFT-G was documented, along with completed treatment for latent TB) or indeterminate but not newly indeterminate, further QFT-G testing will be done according to the Study Plan ([Table 2](#) and [Table 3](#)).

QFT-G testing is performed at least annually and in some cases more often, depending on the result. Refer to the Study Plan ([Table 2](#) and [Table 3](#)).

